## PROTOCOL TITLE: TERTULIAS

participants understand why we have structured the project to have two arms. After viewing the video, participants interested in participating will continue the informed consent process (in English or Spanish, depending on participant preference).

After the presentation is over, those who decide not to participate will then be free to leave the meeting. If the meeting is in-person, those who decide to participate will be asked to approach a table to sign the consent form and research team members at the consent table will do a brief review of the consent. There will not be a waiting period for consent as there is no safety or scientific purpose to a delay. If the meeting is by Zoom, the participant will be told that a member of the team will contact them to obtain consent.

The research team members at the tables or those who obtain consent later will be Spanish-speaking and will ensure that participants understand that their participation is voluntary and that they can choose not to participate or to withdraw their participation at any point in the study. The consent form contains contact information for the PI and for the UNM HRPO in case the participant has a question or concern. Both the participant and the research team member will sign the consent form. The participant will be given a copy of the consent to keep for their files.

Also, we are requesting permission to obtain oral consent from those who are unable to attend an in-person baseline data collection appointment because of COVID-19 restrictions. When we are attempting to schedule the appointment, it may not be feasible to have the data collectors meet with the participant in-person where the consent form would be signed prior to answering baseline survey questions or obtaining the baseline hair sample if the participant answers affirmatively to COVID-19 screening questions (e.g., positive COVID-19 test, contact with a COVID-19 person, recent out-of-state travel, fever or other symptoms of illness). We are attempting to conduct in-person data collection appointments because we need a baseline hair sample in addition to the survey questions. However, if the participant is unable to meet in-person, we do not wish to exclude the participant since the intervention is being conducted by Zoom and there is no further risk of contagion apart from the baseline data collection appointment. Therefore, we will obtain oral consent by phone or Zoom and document the participant's name, the date of consent and the team member who conducted the consent. All of the consenting participants will have attended a 2-hr Zoom meeting where we describe the study and the contents of the consent form in detail and show the randomization video. Following oral consent, we will provide the participant with a printed copy of the consent form by mail. We will conduct the baseline survey by phone or Zoom and we will attempt to schedule the hair sample collection at a later date, if feasible. If not feasible, the lack of hair sample for that participant will be recorded as missing data.

In addition, participants will be asked to fill out a contact information sheet. The contact information will be gathered on a separate sheet that will be kept separately from the demographic data. The contact information will be used to schedule follow-up appointments, for meeting invitations, and for control arm check-in calls.

The consent form requests permission to be allowed to contact the participant if we have a future project that we think might be of interest to them. We will keep their contact information for 5 years after the study ends and after that it will be destroyed.

There will be an option an individual informational session with women who cannot attend the informational meeting or those who choose to do the consent process in private, but we will encourage potential participants to attend the meeting because we believe that for this population, the meeting process will be more culturally appropriate, more engaging and a superior context for

## PROTOCOL TITLE: TERTULIAS

learning about the research than going over the lengthy consent form individually, and because it will also alleviate feasibility concerns.

At interviews and 12-month data collection, we will remind the participant about the study and the consent they signed and answer questions if they have any.

In Y1, we will reconsent the participants with a new consent form and an approved script that reflects the addition of the What's App chat groups in July 2021 prior to the end of the Y1 groups on July 28. We will not begin analyzing the What's App data until re-consenting has been completed. In subsequent years Y2-Y4, this information will already exist in the consent form. Given that we are still operating remotely under COVID-19 safety restrictions, we will use our existing HRPO approval for oral consent in Y1. Because we conduct baseline data collection appointments in-person, subsequent consent will most likely be conducted in-person, except in cases where that is not permissible for COVID-19 safety concerns. The consent form will have an option for the participant to select whether they would like to be part of the What's App chat group—an opt in/opt out. **With those who opt out, they will not be included in the chat group and we will communicate with them directly regarding any logistical information about the meetings.**

In January 2023, we submitted an amendment to the consent form. On the consent form, the interview with a subset of participants was listed under the bullets describing group 2 (the intervention). We have already interviewed 11 intervention participants from Y1 and have decided that we would also like to conduct interviews with some of the control participants to help us contextualize the survey responses from both groups. We are amending the consent form by moving the interview to the bulleted list that describes activities that are or are potentially conducted with participants from both arms. When we call the control participants and invite them to do an interview, we will indicate that we added in these interviews with control participants because we want to understand their experience in the study and so we will be asking them to re-sign the amended consent form at the time of the interview to reflect the fact that they understand and agree to this change.

In addition, we changed the wording in the Spanish version of the consent to re-word the places where participants opt in or out of the WhatsApp chat group and having their name associated with the creative project. We were instructed by the data collectors who invite the participants to sign the consent that this wording was confusing to participants and always had to have more explanation. We believe that the re-wording will clarify that for when we consent Cohort #4 in summer 2023 (the last cohort).

*For the additional survey questions to validate the interim qualitative analysis results:* For Y1 and Y2 participants who have already completed the intervention and completed follow-up data collection, we will reach out to them by phone, text, Zoom, or email and ask them if they would be willing to answer a few more questions. We will use the attached recruitment script. If they are willing, one of the team members will set up the meeting, administer the new questions orally, and record the responses in REDCap using a tablet or laptop. The additional data collection for Y1 and Y2 participants should only take 15-20 minutes. Participants will receive a \$25 merchandise card for answering the additional questions. Because for Y3 and Y4 participants, the questions will be incorporated into the follow-up data collection, we will not offer additional incentive.

## PROTOCOL TITLE: TERTULIAS

We are requesting approval to obtain oral consent for Y1 and Y2 participants to answer these additional questions. They have already signed the consent form for the project. We will document the fact that they consented in REDCap.

### Non-English Speaking Subjects

Because this is a study with FMIs, we anticipate that they will have Spanish as their first language and that many may not speak English well or at all. Fluency in Spanish is a criteria for inclusion in the study, as group sessions will be conducted in Spanish.

All of our project materials, including consent and the recruitment video will be available in English and Spanish. We anticipate that the vast majority of participants will prefer Spanish language materials, but in case they prefer English, both will be available.

All of the data collectors and facilitators who interface with participants in this project have Spanish as their first language. The PI, who will conduct interviews, is fluent in Spanish.

## 27.0 Data Transfer/Sharing

*Complete this section if the research involves transferring/sharing of data with an external entity (institution, company, etc.).*

- A. Will data be transferred/shared with an external entity (institution, company, etc.)?  
 Yes  
 No. **The remainder of this section does not apply.**
- B. Indicate if the data is incoming and/or outgoing: outgoing
- C. Provide the name of the entity that data will be transferred/shared with:  
University of Pittsburgh
- D. Provide the contact name, email and phone number with whom data is being transferred/shared with: [name], [[contact]](mailto:[contact]), [contact]
- E. Who is responsible for transmission of the data? [name]
- F. Who is responsible for receiving the data? [name]
- G. Describe how the data will be transferred/shared. Please note data cannot be transferred/shared without assistance from UNM HSC IT. **Requesting HSC Central IT Transfer is detailed on the Sponsored Projects website:** [name] will have access to REDCap. Data will be downloaded from REDCap and stored on an access-limited, password-protected University of Pittsburgh secured server behind the institution's firewall.
- H. For data being transferred/shared with outside locations or entities, describe the following:
  - Where is data storage and how will it be maintained in a secure manner (i.e. encryption, password protection, use of Qualtrics or REDCap, etc)?

## PROTOCOL TITLE: TERTULIAS

Data downloaded from REDCap will be stored on an access-limited, password-protected University of Pittsburgh secured server behind the institution's firewall.

- What is method in which data will be collected and stored (i.e. electronic, hard copy, etc)? Data will be collected by UNM research personnel and entered directly into UNM's REDCap system.
- How long will the data be stored? The data will be stored on the University of Pittsburgh server for up to 5 years following completion of the study.
- Who will have access to data? Only [name] will have access to the data at the University of Pittsburgh.

I. Please list all specific data elements, variables, etc. to be sent out and/or received. Indicate if the data contains identifiers and health information. Please note that identifiers that MUST be removed to make health information de-identified are as follows: Names, All geographic subdivision smaller than a State, All elements of year (except year), Telephone, Fax numbers, E-mail addresses, Social Security, Medical record number, Health plan beneficiary, Account numbers, Certificate/license numbers, Vehicle identifiers and serial numbers, Device identifiers and serial numbers, Web URLs, IP address numbers, Biometric identifiers, full face photographic images, and Any other unique identifying number, characteristic or code.) Demographic characteristics including DOB, health status (pregnant, whether using medications, sleep quality), questions about experiences with social isolation, discrimination, COVID questions (ever tested, diagnosed, employment/healthcare/lifestyle disruption/changes due to COVID), Center for Epidemiologic Studies Depression Scale (CES-D), Perceived Stress Scale (PSS-14), Connor Davidson Resilience Scale (CD-RISC), Medical Outcomes Study Social Support Survey, Trauma-Informed Practice Scale (TIP), intervention evaluation questions.

J. If the research requires the access, use, or disclosure of any of the 18 individually identifiable protected health information (PHI) identifiers that can be used to identify, contact, or locate a person (e.g., name, medical record number, etc.), are the subjects going to consent to or authorize the disclosure of their individually identifiable health information? Yes

- a. *Or* is HIPAA authorization altered or waived? No

K. What is the classification of the data (de-identified, limited data set, protected health information, other). Limited data set

L. Does the request to transfer/share data include clinical data that belongs to the UNM Health Systems? No

M. Does the data to be transferred/shared include information about patients seen at external health system or at a third party medical provider? No

N. Is the external entity a “covered entity”? yes

O. Is the data that is going to be transferred/shared owned or partially owned by another party or have any type of restrictions including regulatory restrictions (i.e. HIPAA, FERPA, etc.)? no

P. Is the data publically available? If yes, please provide details: no

## PROTOCOL TITLE: TERTULIAS

Q. Does the data include information about substance abuse treatment, sexually transmitted diseases, genetic testing results, HIV/AIDS testing results, and/or mental health? Yes-depression only

## 28.0 Specimen Transfer/Sharing

*Complete this section if the research involves transferring/sharing of specimens with an external entity (institution, company, etc.).*

- A. Will specimens be transferred/shared with an external entity (institution, company, etc.)?
  - Yes
  - No. **The remainder of this section does not apply.**
- B. Indicate if the specimens are incoming and/or outgoing:
- C. Provide the name of the entity that specimens will be being transferred/shared with:
- D. Provide the contact name, email and phone number with whom specimens are being transferred/shared with:
- E. Who is responsible for sending out the specimens? Please note specimens cannot be sent out without a fully executed material transfer agreement.
- F. Who is responsible for receipt of the specimens? Please note specimens cannot be received without a fully executed material transfer agreement.
- G. For specimens being transferred/shared with outside locations or entities, describe the following:
  - *Where is specimen storage and how will it be maintained in a secure manner?*
  - *What is method in which specimens will be collected and stored?*
  - *How long will the specimens be stored?*
  - *Who will have access to the specimens?*

OFFICIAL GRANT TITLE	Addressing Social Isolation to Reduce Depression Among Women of Mexican Origin
STUDY TITLE	Tertulias
NCT IDENTIFIED NUMBER	NCT04254198
FUNDED BY	National Institute on Minority Health and Health Disparities
GRANT NUMBER	5R01MD014153-05
SAP VERSION	1.0
SAP VERSION DATE	June 23, 2024
TRIAL STATISTICIAN	[name]
PROTOCOL VERSION (SAP associated with)	1.0
TRIAL PRINCIPAL INVESTIGATORS	[name]
SAP AUTHOR(s)	[name]

TABLE OF CONTENTS

1	INTRODUCTION.....	4
2	STUDY AIMS AND ENDPOINTS	4
2.1	Study Aims	4
2.2	Outcomes	4
3	STUDY METHODS.....	4
3.1	General Study Design and Plan.....	4
3.2	Intervention Arms	5
3.3	Study Population	5
3.4	Randomization and Blinding	6
3.5	Study Assessments.....	6
3.6	Description of Variables.....	7
4	SAMPLE SIZE	8
5	GENERAL ANALYSIS CONSIDERATIONS.....	8
5.1	Timing of Analyses	8
5.2	Analysis Populations.....	8
5.3	Covariates and Subgroups	8
5.4	Missing Data.....	8
5.5	Summary of Study Data	9
5.6	Subject Disposition	9
5.7	Protocol Deviations	9
5.8	Outcome Analyses.....	9
5.9	Baseline Descriptive Analyses	9
5.10	Primary Outcome Analysis.....	9
5.11	Secondary Outcome Analyses.....	10
5.12	Exploratory Outcome Analyses	11
5.13	Sub-Group Analyses.....	11
5.14	Post-Hoc Analyses.....	11

5.15	Safety Analyses.....	11
6	REFERENCES.....	13

1 Introduction

We will conduct a randomized controlled trial of “Tertulias,” an innovative social isolation peer support group model, with 240 women of Mexican origin to contribute to the science of a holistic, multi-level (individual, family, and group) intervention to reduce health disparities related to social isolation and depression among this population. Our transdisciplinary team will use a rigorous, mixed-methods, community-engaged approach that includes a cutting-edge biological assessment of hair cortisol as a biomarker for chronic stress.

2 Study Aims and Endpoints

2.1 Study Aims

- 2.1.1** To measure whether a culturally situated peer group intervention will reduce depression and stress associated with the experience of immigration.
- 2.1.2** To test whether an intervention using a “women’s funds of knowledge” approach results in improved resilience, knowledge and empowerment.
- 2.1.3** To investigate whether a culturally situated peer group intervention using a women’s funds of knowledge approach can give participants’ a sense and experience of social and physical connection (“emplacement”) that is lost in the process of immigration.

2.2 Outcomes

The objectives described above will be measured with the following endpoints. Intervention arms are described in Section 3.2.

2.2.1 Primary Outcomes

The primary endpoints are changes from baseline to 12 months in:

- 2.2.1.1** Depression as measured by the Center for Epidemiologic Studies Depression Scale (CES-D)^{1,2}
- 2.2.1.2** Resilience as measured by the Connor-Davidson Resilience Scale-25 (CD-RISC 25)³
- 2.2.1.3** Social support as measured by The Social Support Scale (MOS-SSS)⁴

2.2.2 Secondary Outcomes

- 2.2.2.1** Changes in stress from baseline to 12 months as measured by the Perceived Stress Scale-14 (PSS-14)⁵
- 2.2.2.2** Knowledge and empowerment in the intervention arm only at 12 months, measured by the Trauma-Informed Practice Scale (TIPS)^{6,7}
- 2.2.2.3** Changes from baseline to 12 months in social connectedness as measured by Social Network Analysis⁸

2.2.3 Exploratory Outcomes

- 2.2.3.1** Changes in hair cortisol levels from baseline to 12 months

3 Study Methods

3.1 General Study Design and Plan

This is a multisite randomized controlled trial (RCT) assessing the effectiveness of the Tertulias intervention for women of Mexican origin as compared to usual care. Participants will be recruited from the community in Albuquerque, New Mexico. They must be women who are 18 years or older, speak Spanish fluently, and have income <250% of the Federal Poverty Limit. We will advertise at

community locations, focusing on two sites in Albuquerque, NM, and invite potential participants to join a live informational Zoom session to learn more about the project. If eligible and interested, the participant will be consented and randomized to one of the two arms. Within four weeks of randomization the participant will be contacted to complete the baseline interview. One year following enrollment, participants will complete a 12-month interview. See Figure 1 for the study CONSORT diagram. Primary and secondary outcomes measures are obtained from follow-up interviews.

3.2 Intervention Arms

3.2.1 Arm 1: Control

Using a modified Attention Control Placebo (ACP) design to reduce attrition over the 12 months, control arm participants will receive a bimonthly phone call from our project coordinator to check in with them, make sure their contact information is correct, and let them know that the study is continuing.

3.2.2 Arm 2: Intervention

We will conduct Tertulias structured dialogue groups using the model we developed and tested through our preliminary research (see [name] et al. 2021).⁹ Each group will have approximately 10 women and will meet weekly for 2 hours over a 12-month period. Group meetings will be conducted in Spanish, led by a team of two FMI facilitators using our structured dialogue approach. Because of required safety restrictions related to the COVID-19 pandemic, our original intention to hold these groups in-person was amended to hold the groups remotely by Zoom. We will work further with each Arm 2 participant to ensure that they know how to use Zoom and have electronic access.

[figure not shown]

Figure 1. CONSORT diagram for the Tertulias study.

3.3 Study Population

3.3.1 Inclusion Criteria

To be eligible to participate in this study, an individual must meet all of the following criteria:

- Adult women 18+
- Born in Mexico
- Speak Spanish fluently
- Self-report income under 250% FPL

3.3.2 Exclusion Criteria

Anyone who is incarcerated or who does not meet the inclusion criteria will be excluded.

3.4 Randomization and Blinding

3.4.1 Randomization

Participants will be randomized to either the Tertulias intervention or usual care. A stratified, block randomization design will be used to stratify by site and cohort (year) with randomly permuted block sizes of 4, 8, and 12. The intervention arm allocation will be programmed in R 4.0 or higher using the package `blockrand`¹⁰ and outputted as a .CSV file. A digital allocation plan will be provided to a research team member where they recorded the participant's name into each assignment. This file will be stored on a secured computer accessible only by that particular research team member. The treatment arm will be recorded in REDCap. Enrollment will be continuous with the goal of reaching the target sample size. Some sites may enroll more or less than the target for each arm.

3.4.2 Blinding

This is an unblinded study. Research staff will only have access to blinded reports with treatment groups indicated by "Arm A" and "Arm B" until the final analysis is performed.

3.5 Study Assessments

3.5.1 Data Collection

We will gather data through in-person data collection appointments at baseline and 12 months. Data collection appointments will be in-person in order to gather hair samples unless there are safety concerns (e.g., COVID-19 illness in the participant's home, a COVID-19-positive test within the past 2 weeks, fever, cough, travel outside the state within the past 14 days, etc.). In the case of participants with these concerns, we will conduct the survey by phone and gather the hair sample at another time if resolution of the concern is able to be made within the timeframe of a week after starting the meetings. All in-person data collection appointments will be conducted using COVID-19 safety procedures involving screening questions, temperature check, hand sanitizer, and face masks for both the data collector and the participant. Additionally, data collectors will also wear face shields, gloves, and shoe covers.

3.5.2 Study Assessments

3.5.2.1 Baseline

We will collect basic participant characteristics such as age, marital status, education level, employment status, number of children, number of family living in their location, whether they speak English, and overall health status. Additionally, we administer the CES-D (depression), the CD-RISC (resilience), the MOS-SS (social support), and PSS (perceived stress) instruments, as well as questions about their social networks. We will also collect hair samples (see [name] et al. 2021).⁹

3.5.2.2 12-month follow-up

We will administer the CES-D (depression), the CD-RISC (resilience), the MOS-SS (social support), PSS (perceived stress), and the TIPS (empowerment) instruments (Tertulias group only). Additionally, we will ask questions about their social networks and collect hair samples.

3.5.3 Visit Windows

Participants are randomized, and hence considered enrolled, following completion of consent and the baseline interview. The 12-month follow-up assessment occurs within a 4-week window starting at 12 months post-baseline. After the 4-week window, participants will be considered lost to follow-up.

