## 9.0 Procedures Involved\*

### QUANTITATIVE DATA COLLECTION:

■) **Surveys**. We will administer a multi-dimensional pre/post survey to all participants at baseline prior to the first group session and at 12-months. The survey will combine demographic questions with questions from validated instruments to measure domains of interest (Depression, Stress, Resilience and Adaptability, and Social Support) plus questions to document the participant's social network to measure social connectedness to inform the social network analysis (see Table and attachments). **At baseline**, all participants will also be asked demographic questions. **At baseline and 12 months**, all participants will be asked the pre/post survey questions. **At 12 months**, Arm 1 (*control*) participants will be asked to answer questions about interest in participating in an intervention group, and Arm 2 (*intervention*) participants will also be asked a series of questions designed to evaluate their participation in and perspective on the TERTULIAS intervention, including the Trauma-Informed Practice Scale to measure Empowerment and Knowledge. **At each time point**, data collection appointments will be in-person because of the need to gather hair samples and will follow COVID-19 guidelines as appropriate related to screening questions, temperature screening, face masks, social distancing as much as possible, and use of sanitizing products. The survey will be administered

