### Retrospective pre-test design

We want to validate the qualitative data analysis because it seems to align with the experience people report and that we observed, while the preliminary results of the survey data analysis do not align with what we have observed or what people report. To deal with this misalignment, we consulted with a methodologist who suggested we use a “retrospective pre-test design” and administer some new questions. With this method, we will use the qualitative results as the constructs for the new questions. Each question will get asked at the 12-month follow-up in 2 ways using this format on a scale of 1-5:

1. Before you started Tertulias, how would you rate your knowledge of resources in the community?
2. When you finished Tertulias, how would you rate your knowledge of resources in the community?
3. Before you started Tertulias, how would you rate your confidence using technology such as Zoom?
4. When you finished Tertulias, how would you rate your confidence using technology such as Zoom?
5. Before you started Tertulias, how lonely or socially isolated did you feel?
6. When you finished Tertulias, how lonely or socially isolated did you feel?
7. Before you started Tertulias, how much of a sense of belonging did you feel?
8. When you finished Tertulias, how much of a sense of belonging did you feel?

The literature suggests that this format of question asked at follow-up tends to elicit more truthful responses from participants. We will compare these responses with answers to the validated instrument questions and to the qualitative data.

We will add these questions to the 12-month follow-up survey and administer them to all of the Y3 and Y4 participants as part of the 12-month data collection. We will be gathering follow-up data from Y3 participants in July/August of this year and from Y4 participants in July/August 2024.

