### Study Timeline

Study Year	Month	Activity
Year 1	1.	Hire Data Collectors, Train Staff (CITI, COI, HIPAA), Create Protocols
	2.	Create contract with local filmmaker for randomization video (a filmmaker has been identified)
	3.	Produce randomization video conclude team certifications.
	4.	Recruit for COHORT #1 Consent, Randomize & Baseline
	5.	
	6.	
	7.	COHORT #1 GROUPS
	8.	
	9.	
	10.	
	11.	
	12.	
Year 2	1.	Conduct Interviews
	2.	
	3.	
	4.	
	5.	
	6.	

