## PROTOCOL TITLE: TERTULIAS

	7. 8. 9. 10. 11. 12.	COHORT #2 GROUPS	COHORT #1 Post Survey
	Conduct Interviews Analyze QUALE data from COHORT #1		
Year 3	1. 2. 3. 4. 5. 6.		Recruit for COHORT #3 Consent, Randomize & Baseline
	7. 8. 9. 10. 11. 12.		COHORT #2 Post Survey
	Conduct Interviews Analyze QUALE data from COHORT #2		
	1. 2. 3. 4. 5. 6.		Recruit for COHORT #4 Consent, Randomize &
Year 4	7. 8. 9. 10. 11. 12.	COHORT #3 GROUPS	COHORT #3 Post Survey
	Conduct Interviews Analyze QUALE data from COHORT #3		
	1. 2. 3. 4. 5. 6.		COHORT #4 Post Survey Analyze Meeting Transcripts, Observation Notes, Logs & Participant shared notebooks from COHORT #3
	7. 8. 9.		Analyze QUALE data
	10. 11. 12.		Create matrices QUALE & QUALE data Triangulate Final Analysis

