5.7 Protocol Deviations

Reported protocol deviations are missed visits and visits that occurred beyond the defined window period (+ 60 days from target date). We will report the total number of deviations and the frequency and percentage of each reason. Individual listings will also be produced.

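### The 12-month window runs from each woman's own baseline while groups and surveys follow a cohort calendar, so it can close before an Arm 2 woman's intervention ends

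*SAP*

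**What the plan says.** **The individual clock.** SAP 3.5.3 sets the window: "The 12-month follow-up assessment occurs within a 4-week window starting at 12 months post-baseline". It then adds: "After the 4-week window, participants will be considered lost to follow-up". SAP 3.1 also counts from the individual, though from enrollment: "One year following enrollment, participants will complete a 12-month interview". SAP 5.7 uses a different limit and reports as deviations "visits that occurred beyond the defined window period (+ 60 days from target date".

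**The cohort clock.** Protocol 21.0 (Arm 2) has groups meeting weekly for 12 months. In the Study Timeline, "Recruit for COHORT #1 Consent, Randomize & Baseline" is entered at month 4 of Year 1, the cohort 1 groups at month 7, and "COHORT #1 Post Survey" appears from month 7 of Year 2. The table layout is broken in the available text, so these months are a reading of it. Protocol 9.0 (What's App) ends the Y1 groups on July 28. Follow-up is dated for whole cohorts: "We will be gathering follow-up data from Y3 participants in July/August of this year", with Y4 in July/August 2024.

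**The only link.** Protocol 9.0 (Surveys) places the survey "at baseline prior to the first group session and at 12-months". This fixes the order of baseline and first session but not the distance between them.

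**The concern.** If baseline comes well before the first session, a woman reaches 12 months by the SAP's clock while her groups are still meeting. The site can then do one of two things.

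- **Interview her inside the window.** She is measured before the intervention is complete. Protocol Aim 2 intends the TIP scale for after the intervention, and the added retrospective items ask women to rate themselves as of when they finished Tertulias. Neither fits a visit made while groups are running.
- **Interview her after the groups end.** SAP 3.5.3 already calls her lost, although a valid interview exists. The disposition summary in SAP 5.6 would then understate retention. The SAP would also give two answers for, say, a visit on day 40 of the window: lost under 3.5.3, not yet a deviation under 5.7.

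All three primary outcomes and the PSS-14 come from this visit. Protocol 9.0 (Additional Survey Questions) reports that a preliminary comparison at the end of Y2 found little or no difference between arms. The rule for which interviews count should therefore be settled before the final data are analysed.

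**Working it through.** **The plan's own figure.** Protocol 7.0 ends the intervention in month 6 of Y5. Taking the cohort 1 pattern (groups from month 7 of the study year), cohort 4 starts in study month 3 × 12 + 7 = 43. Twelve months of groups end in study month 43 + 12 − 1 = 54, which is month 6 of Y5. The calendar reproduces.

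**When the window closes first.** Let L be the days from baseline to first session.

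- The window closes 12 months + 28 days after baseline (SAP 3.5.3).
- Groups end 12 months + L days after baseline.
- The window therefore closes before groups end whenever L > 28. With SAP 5.7's limit, the condition is L > 60.

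On the planned timeline, L can reach about 3 months (91.3 days). The earliest window then closes 91.3 − 28 = 63.3 days, about 9 weeks, before groups end. A woman interviewed exactly at 12 months would have had 9/12 × 52 = 39 of 52 weekly sessions.

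**Share of Arm 2 affected.** The documents give no distribution of baseline dates. Assume they spread evenly over the D days before group start, in every cohort. The share is max(0, (D − w)/D), with w = 28 or 60. Counts use 126 women in Arm 2 (Protocol 4.0; 252/2).

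| D (days) | w = 28 | w = 60 |
|---|---|---|
| 28 | 0% | 0% |
| 42 | 14/42 = 33% (42 women) | 0% |
| 61 | 33/61 = 54% (68) | 1/61 = 2% (2) |
| 91.3 | 63.3/91.3 = 69% (87) | 31.3/91.3 = 34% (43) |

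**Survey date, both arms.** If the cohort is surveyed s days after groups end, the share past the 28-day window is min(1, (D + s − 28)/D). For D = 91.3 this is 69% at s = 0, 86% at s = 15 and 100% at s = 30.

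**Dated calendar.** Assume groups end on July 28 in every cohort and surveys can start on July 1.

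| Baselines spread evenly over | Window closes before July 28 | Window closes before July 1 |
|---|---|---|
| July 1 to 28 | 0% | 0% |
| June 21 to July 28 | 24% | 0% |
| June 1 to July 28 | 50% | 3% |
| April 28 to July 28 | 69% | 39% |

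Even in the July 1 to 28 case, windows close between July 29 and August 25. By August 15, 17 of the 28 baseline dates (61%) are past their window, while the protocol schedules follow-up through August.

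**The case against.** The three-month gap rests on one planning timeline with a tentative start date, and its table is hard to read. Baseline is the last of the steps in that entry, so interviews need not begin on the first day of month 4. The dated passages point to a shorter gap: Protocol 9.0 puts Y3 baseline in summer 2022, and Protocol 26.0 puts cohort 4 consent in summer 2023, about a year before that cohort's July/August 2024 follow-up. This stands. It is why the share cannot be stated more closely than 0% to about 69%.

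A reader might infer that late interviews would be dropped from the analysis. The documents do not say so. The per-protocol population in SAP 5.2.2 requires a completed 12-month interview and names no window, the ITT population in SAP 5.2.1 does not depend on follow-up, and SAP 5.7 lists late visits as deviations. The stated consequence is a disposition label, and the SAP leaves its effect on the analysis unsettled.

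A reader might also count both arms, about 175 of 252. That overstates the group-end problem, because only Arm 2 attends groups. Nor does follow-up always come after the groups: Protocol 7.0 and 8.0 put the end of the intervention and the last follow-up in the same month.

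Finally, a baseline anchor agrees with SAP 2.2.1, which defines the primary endpoints as change from baseline to 12 months. Moving the anchor is therefore partly a choice. What the objection does not remove is that the two clocks are never linked and that any gap above 4 weeks puts them in conflict.

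**Conclusion.** The concern holds as a conflict of rules whose size is unknown. The window and lost-to-follow-up status follow the individual baseline, the intervention and surveys follow the cohort, and nothing caps the distance between them. The upper figures assume that the planned timeline applied to all four cohorts with an even spread of baselines.

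Two stronger readings are not supported. One is that many women are affected: this needs baseline dates that the documents do not give. The other is that most windows close before surveys can begin: with June or July baselines and surveys from July 1, that share is 0% to 3%, although surveys held late in August would still miss windows in both arms.

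This should be fixed, because a written rule can label valid post-intervention interviews as lost or call for interviews while groups are running. It does not by itself invalidate the primary analysis.

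**What to change.** Before database lock, reconcile SAP 3.5.3 and 3.1 with SAP 5.7 and with the cohort calendar in the protocol:

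1. State that any completed 12-month interview is kept in the primary analysis and is not classed as lost to follow-up because of its distance from the woman's own baseline.
2. Set the target date by the same rule in both arms, so that it does not fall before the cohort's groups end. Measure one window and one deviation limit from that date.
3. Derive months from baseline to interview, report it by arm, and give one sensitivity analysis limited to interviews 12 to 14 months after baseline.
4. While editing, settle the order of baseline and randomization, on which SAP 3.1 and 3.5.3 disagree.

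The cost is SAP wording, one derived variable and one extra model run. It assumes that interview dates are recorded. The protocol describes attendance tracking and weekly meeting logs, but does not mention interview dates. The downside is that the baseline-to-follow-up interval may exceed 12 months for early enrollees in both arms, which item 3 makes visible.
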